1.1 Background of Trial Plan

Acute myeloid leukemia (AML) is a malignant disease derived from myeloid hematopoietic cells. In AML, unregulated proliferation of leukemia cells is associated with inhibition of normal hematopoiesis. AML is a life-threatening disease with various symptoms such as infection, anemia, hemorrhage due to thrombocytopenia, and organ disorders. Although AML occurs in people of all ages, it is known to be more prevalent among the elderly, and the median age of onset is reported to be 62 years in Japan.¹ Treatment of AML is based on the concept of total cell kill. Normally, after complete remission (CR) is achieved by remission induction therapy to reduce leukemia cell count to below 10^9 cells, consolidation therapy is performed to further reduce the number of residual leukemia cells to near zero.² However, it is not rare for patients, especially elderly patients, to experience relapse due to proliferation of residual leukemia cells after CR. The prognosis for AML becomes worse as age increases. There are many reasons for this. For one, the deterioration in organ functions (including bone marrow, liver, cardiorespiratory and renal functions) in the elderly constitutes a barrier to adequate AML therapy. Also, AML in elderly patients more frequently arises from antecedent hematologic disorders such as myelodysplastic syndrome (MDS), which is always associated with a worse outcome. Moreover, elderly AML patients have a higher incidence of poor-risk cytogenetics, which is associated with poor outcome. In an investigation involving elderly AML patients (aged 50 to 70 years) not receiving allogeneic hematopoietic cell transplantation, even for those patients who achieved CR, the 3-year relapse-free survival (RFS) was as low as 29% and many patients experienced relapse.³ When treating elderly patients with antitumor drugs, it may be necessary to reduce the dose. There are a considerable number of limitations and much debate regarding therapeutic regimens in elderly patients with leukemia. Therefore, a new therapy is needed to prevent relapse of AML, and extend survival of elderly patients with AML.

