6.3 Method of Minimizing or Avoiding Bias

The treatment allocation code will be double-blinded during the treatment period, meaning neither the investigator nor the subject will know whether the treatment administered is OCV-501 or placebo. The sponsor's trial personnel, such as those involved in monitoring, data management, and data analysis, including personnel belonging to contract research organizations (CROs), will not have access to the treatment allocation code during the conduct of the trial. Only the subject randomization center will have access to the treatment allocation code for this trial, and only if it is needed in an emergency.

OCV-501 vials and placebo vials will be indistinguishable in appearance and shape.

Blinding is critical to the integrity of this trial. However, in the event that a subject experiences a medical emergency in which knowledge of the IMP is critical to the subject's management, the blind may be broken by the investigator. The need to break the blind must first be discussed with the sponsor and the best method to do this will be determined. The treatment allocation code should be kept confidential and revealed only to those individuals that must be informed for medical management of the subject. See Section 8.2.4 for procedural details.

For measurement of the OCV-501-specific IFN- γ production, WT1-killer peptide specific IFN- γ production, anti-OCV-501 antibody level, and anti-WT1 antibody level, the results will not be revealed until unblinding at conclusion of the trial. If a medical emergency occurs in a subject and knowledge of his or her IMP randomization code is considered important for treatment, the emergency code will be broken according to Section 8.2.4, [Emergency Code Breaking \(Procedure for Unblinding During the Trial Period\)](#).

The randomization will be stratified by two stratification factors: country/region (Japan, Republic of Korea, Taiwan), and age at the time of providing informed consent (60 to 64 years, 65 to 70 years, and ≥ 71 years) to minimize imbalances between the treatment arms.

7 Trial Procedures

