11.3.1.1 Primary Endpoint

1) Definition

- Disease-free survival (DFS)
 - Observation period: For each subject, the time from randomization to the DFS-cutoff date. The DFS-cutoff date was set as the completion date of each subject.
 - Definition: The time from randomization until relapse or death from any cause, whichever comes first by the DFS-cutoff date.
 - Event: Relapse or death from any cause by the DFS- cutoff date.
 - Censoring:
 - If an event has not been observed by the DFS-cutoff date, then the last confirmed non-relapse date will be used as the censoring date.
 - For subjects who have withdrawn from this trial before the completion date for reasons other than relapses or deaths, if non-relapse has been confirmed on the withdrawal date, then the withdrawal date will be used as the censoring date.

2) Analysis Set

FAS, PPS

3) Analysis Method

Primary method: Kaplan-Meier curve, log-rank test

The Kaplan-Meier method will be carried out to estimate DFS functions and plot the DFS curve by treatment arm.

- The log-rank test will be used to determine whether there are differences at the 5% significance level in DFS between the OCV-501 treatment arm and the placebo arm.
- The hazard ratio (OCV-501 vs. placebo) and its 95% confidence interval will be calculated using the wald test.
- The 2-year survival rate and median survival time will be calculated and 95% CI of survival rate will be calculated using the Greenwood formula.

Exploratory method:

- Harrington-Fleming Test: applying the weight $1-S(t)$, where $S(t)$ is calculated from Kaplan Meier survival estimate.
- HR and its 95% CI will be calculated at every 3-month interval. The hazard rate will be calculated using the person-year method by treatment arm.
- The Cox PH (Proportional Hazards) model will be used to adjust treatment comparison for a set of covariates which are set to be country (each country) and age (60 to 64 years, 65 to 70 years, and ≥ 71 years) on the time-to-event variable. Also, the assumption that the hazard ratio is constant over time will be graphically assessed by looking at the log-minus-log survival plots with stratification of covariates.

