4.7.1 Primary Efficacy Endpoints

4.7.1.1 Disease-free Survival

1) Definition:

- Observation period: For each subject, the time from randomization to the DFS-cutoff date. The DFS-cutoff date was set as the completion/discontinuation date of each subject.
- DFS: The time from randomization until relapse or death from any cause, whichever comes first by the DFS-cutoff date.
- Event: Relapse or death from any cause by the DFS-cutoff date.
- Censoring:
 - If an event has not been observed by the DFS-cutoff date, then the last confirmed non-relapse date will be used as the censoring date.
 - For subjects who have withdrawn from this trial before the completion date for reasons other than relapses or deaths, if non-relapse has been confirmed on the withdrawal date, then the withdrawal date will be used as the censoring date. Otherwise, the last confirmed non-relapse date will be used as the censoring date.

2) Analysis Set:

FAS (primary), PPS

For the judgment of relapse by the central pathological review committee, DFS will be evaluated in the FAS and PPS as primary analysis.

For the judgment of relapse by trial site, DFS will only be evaluated in the FAS as secondary analysis.

3) Analysis Method:

- Primary test for comparison between OCV-501 and Placebo will be conducted by Log-rank test. For exploratory purposes, the Harrington-Fleming (HF) test will be performed by applying the weight $1 - \hat{S}(t)$, where $\hat{S}(t)$ is the product-limit estimates of survival functions.
- Kaplan-Meier estimate of survivor function $\hat{S}(t)$ and curve

$$\hat{S}(t) = \Pr(\text{Survive beyond } t)$$
$$= \prod_{j: t_j < t} \left(\frac{n_j - y_j}{n_j} \right)$$

where t_j is the j -th event time, n_j is the number of patients at risk and y_j is the number of events.

The Kaplan-Meier curve plots the estimated survival function $\hat{S}(t)$ vs. time separately for each treatment arm.

- The 2-year survival rate and median survival time will be calculated. The 95% CI of the 2-year survival rate will be calculated using Greenwood formula.
- Hazard ratio (HR) and its 95% CI will be calculated from the Cox proportional hazards model.

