 - In the model of Cox analysis, treatments effect will be adjusted with covariates (Age, Country/Region and WT1 mRNA level at Day 1). The model with covariates (WT1 mRNA only) or model without covariates will be also analyzed. In these models, age will be categorized into 3 groups (60 to 64 years, 65 to 70 years, ≥ 71 years), Country/Region into 2 groups (Japan, Republic of Korea+Taiwan), WT1 mRNA into 4 groups (<50, 50-199, 200<= and Unknown).
 - BRESLOW method will be used for ties.
 - Proportionality assumption in Cox proportional hazard model will be assessed using 2 methods:
 - 1) SAS PHREG procedure ASSESS PH option will be used for checking proportional hazard assumption.
 - 2) Look at the log-minus-log survival plots graphically. If the graph results in parallel lines then the proportionality assumption is satisfied.
- HR and its 95% CI at every 3 months interval will be calculated by adding a time varying covariate to Cox Proportional Hazards model as an alternative analysis if the proportionality assumption fails. The model will be as follows:

$$\lambda(t;X) = \lambda_0(t) \exp(\beta_1 \text{trt} * \text{period}_1 + \beta_2 \text{trt} * \text{period}_2 + \dots)$$

where $\lambda_0(t)$ is the baseline hazard function,

trt is the treatment arm(1= OCV-501 and 0= Placebo) and

$$period_1 = \begin{cases} 1 & \text{if } 0 \leq DFS \text{ time} < 3 \text{ Months} \\ 0 & \text{otherwise} \end{cases}$$

$$period_2 = \begin{cases} 1 & \text{if } 3 \leq DFS \text{ time} < 6 \text{ Months} \\ 0 & \text{otherwise} \end{cases}$$

...

So HR (OCV-501 vs. Placebo) for each period will be calculated as follows:

$$\lambda(\text{OCV-501}|\text{period}_k) = \lambda_0(t)\exp(\beta_k)$$

$$\lambda(\text{Placebo}|\text{period}_k) = \lambda_0(t)$$

$$\text{HR}(\text{OCV-501 vs. placebo}|\text{period}_k) = \lambda_0(t)\exp(\beta_k) / \lambda_0(t) = \exp(\beta_k)$$

$$95\% \text{ CI} : [\exp(\beta_k - 1.96 * \sqrt{\text{Var}(\beta_k)}), \exp(\beta_k + 1.96 * \sqrt{\text{Var}(\beta_k)})]$$

- For exploratory purposes, the incidence rate over the entire follow-up period will be calculated using the person-year method by treatment arm as follows.

- 1) Calculate the number of events and person-year at risk by treatment arm.
- 2) Calculate the incidence rates and its corresponding 95% CI by treatment arm. (1 year is calculated as 365.25 days)

$$\text{Rate} = \frac{\text{Number of events}}{\text{Person - year}}$$

95% CI:

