4.7.2 Secondary Efficacy Endpoints

4.7.2.1 Overall Survival

1) Definition:

- Observation period: For all subjects, the time from randomization to OS-cutoff date. The OS-cutoff date was set as the date after 728 days (2 years) from the day that the last subject started IMP administration without consideration of withdrawal by the OS-cutoff date.

- Definition: The time from randomization until death from any cause by the OS-cutoff date.
- Event: Death from any cause by the OS-cutoff date.
- Censoring: If an event has not been observed by the OS-cutoff date, then the last confirmed survival date will be used as the censoring date.

2) Analysis Set:

FAS, PPS

3) Analysis Method:

The same analysis will be conducted as for DFS.

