4.13 Changes in the Conduct of the Study or Planned Analysis

Any changes made after the database lock will be recorded in the relevant section of the clinical study report.

Changes from the analysis planned in the protocol are as follows:

Section number	Contents of changes	Reason of changes
4.5 Demographics and Other Basic Characteristics	WT1 mRNA level at Day 1 was added instead of AML diagnosis or at the time of induction therapy or consolidation therapy.	Day 1 data would be more influential than the data at diagnosis or at the time of induction or consolidation therapy.
4.7.1.1 DFS 4.7.2.1 OS	Proportionality assumption will be tested first. Cox PH model will be conducted on every 3 month interval as an alternative analysis.	If proportionality assumption fails, then Cox PH model might be considered invalid to conduct on the whole period.

Section number	Contents of changes	Reason of changes
4.7.1.1 DFS 4.7.2.1 OS	Age, country and other factor (WT1 mRNA) will be adjusted as covariates in the Cox PH model. Furthermore, subgroup analysis will be conducted.	Cox PH model analyses adjusted by covariates are added to investigate the influence of covariates. And the subgroup analyses are added as supplementary analyses.
4.7.2.2 QOL	Mixed-effect model repeated measures will be conducted.	To make a comparison on QOL between two treatment arms.
4.7.2.3 PS	Improvement factor will be created and Wilcoxon 2-sample test will be conducted.	To make a comparison on PS between two treatment arms.
4.7.3. Reference efficacy endpoint 4.7.3.1 DFS until OS cutoff date 4.7.3.2 Therapeutic Response	New efficacy variables have been added.	For the purpose of reference
4.8.2 Adverse Events	A summary of SAEs by severity is not conducted.	Listing will cover it.
4.10 Exploratory Items Analysis	For WT1 mRNA item, t-test is not conducted.	According to the nature of WT1mRNA data, comparison between treatment arms will not be necessary.
4.11 Subgroup analysis	Safety and immune response have been added to the subgroup analysis.	For the purpose of reference

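### Randomisation is stratified by region and age, but the primary DFS and OS log-rank tests name no strata, and the SAP does not say which of its three Cox models gives the main hazard ratio

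*SAP*

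**What the plan says.** **Allocation.** Protocol 6.3: "The randomization will be stratified by two stratification factors: country/region (Japan, Republic of Korea, Taiwan), and age at the time of providing informed consent". The age groups are 60–64, 65–70 and 71 or older, so there are 3 × 3 = 9 cells.

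**Test.** Protocol 11.3.1.1: "The log-rank test will be used to determine whether there are differences at the 5% significance level in DFS". SAP 4.7.1.1: "Primary test for comparison between OCV-501 and Placebo will be conducted by Log-rank test". Neither names strata. Protocol 11.3.1.2 plans the OS log-rank test in the same way, and SAP 4.7.2.1 says "The same analysis will be conducted as for DFS". Age and region enter only as Cox covariates and as subgroup factors.

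**Estimate.** Under its primary method, Protocol 11.3.1.1 says "The hazard ratio (OCV-501 vs. placebo) and its 95% confidence interval will be calculated using the wald test", with no covariates mentioned. The Cox model adjusted for country and age is listed under the exploratory method. SAP 4.7.1.1 first describes a Cox model adjusted for age, region and Day 1 WT1 mRNA, then adds: "The model with covariates (WT1 mRNA only) or model without covariates will be also analyzed". No model is called the main one. SAP 4.13 gives the reason "Cox PH model analyses adjusted by covariates are added to investigate the influence of covariates" and does not say whether the main hazard ratio changes.

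**The concern.** There are two separate issues.

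1. **Efficiency of the test.** Stratified allocation balances the arms on age and region. If those factors affect DFS, the unstratified log-rank variance still includes between-stratum variation that the design has removed, so the test is conservative. Protocol 1.1 makes age a plausible factor ("The prognosis for AML becomes worse as age increases") but gives no hazard ratio. With planned power of only 53–75%, a few points are worth having.

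2. **Which hazard ratio is reported.** The order of the SAP text leans towards the fully adjusted model, and the protocol leans towards no covariates. None of the SAP models is the protocol's country-and-age model: each adjusted one includes WT1, and region is pooled to two levels. SAP 4.13 declares the WT1 addition but not the pooling. If one interval excludes 1 and another does not, the plan does not say which to emphasise. This does not affect the result of the primary test.

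**Working it through.** **Step 1: the plan's own power (Protocol 11.5, SAP 4.12).** Inputs: placebo 2-year DFS 20%; OCV-501 35% or 40%; exponential times; 60 per arm; two-sided 5%. Follow-up of about 2 years per patient is from Protocol 3.2.

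- Hazard ratio = ln(S_OCV)/ln(0.20): ln 0.35/ln 0.20 = 0.652; ln 0.40/ln 0.20 = 0.569.
- Events by 2 years: 60 × (0.80 + 0.65) = 87; 60 × (0.80 + 0.60) = 84.
- Schoenfeld power = Φ(|ln HR| × √events / 2 − 1.96): Φ(0.4273 × 9.327/2 − 1.96) = 51.3%; Φ(0.5633 × 9.165/2 − 1.96) = 73.3%.

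Both are within 2 points of the stated 53% and 75%. Freedman's formula with one year of accrual plus two years of follow-up gives 53.8% and 75.2%. The calculation has no stratification term.

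**Step 2: log-rank with and without strata.** 12,000 simulated trials per cell, 120 patients, 2-year follow-up, no dropout. Assumptions not in the documents:

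- permuted blocks of 4 within the nine cells;
- Japan/Korea/Taiwan 70/35/15 (the documents give at most 70 for Japan and about 50 for Korea and Taiwan together);
- age split 30/40/30%;
- age hazard ratios 1/1.3/1.7 (weak), 1/1.5/2.2 (moderate), 1/2/3 (strong), with Korea + Taiwan hazard ratios of 1.15, 1.3 and 1.5.

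The within-stratum treatment hazard ratio was solved so that the overall 2-year DFS stays at 20% versus 40% or 35%. It was 0.569/0.652 (none), 0.560/0.644 (weak), 0.548/0.632 (moderate) and 0.526/0.612 (strong). The stratified test uses six strata: three age groups × Japan versus Korea + Taiwan.

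| Prognostic effect | Power at 40%: plain vs stratified | Power at 35%: plain vs stratified | Type I error: plain vs stratified |
|---|---|---|---|
| None | 73.3 vs 71.6% (−1.7) | 51.0 vs 49.4% (−1.6) | 5.2 vs 5.1% |
| Weak | 74.3 vs 74.2% (−0.1) | 52.3 vs 52.4% (+0.1) | 4.8 vs 4.9% |
| Moderate | 75.6 vs 77.4% (+1.8) | 52.4 vs 54.7% (+2.3) | 4.1 vs 4.8% |
| Strong | 76.8 vs 81.1% (+4.3) | 53.3 vs 59.9% (+6.6) | 3.6 vs 5.1% |

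The Monte Carlo standard error of a power figure is at most √(0.25/12,000) = 0.46 points.

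**Step 3: six or nine strata.** Six strata are 0.9–1.4 points more powerful than nine. The smallest expected stratum is 50 × 0.30 = 15 patients with six strata and 15 × 0.30 = 4.5 with nine.

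**Step 4: sensitivity to the set-up.** A second simulation (6,000 trials per cell) fixed the within-stratum hazard ratio at 0.569 or 0.652 instead of the overall DFS rates. It used a 70/25/25 country split, equal age groups, log hazard ratios of 0 to 0.7 per age step and for Japan, and all nine strata. Stratifying changed power by about −3 to +12 points, and the plain test's type I error fell from 5.0% to 2.8%. The direction is the same; the size depends on the assumptions.

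**Step 5: the three Cox models.** 3,300 trials per cell, the Step 2 scenarios plus an assumed WT1 effect. WT1 shares were 55/20/20/5% (<50, 50–199, ≥200, unknown), with hazard ratios 1/1.2/1.5/1.2 (weak), 1/1.5/2.5/1.3 (moderate) and 1/2/4/1.5 (strong).

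- At planned 40% versus 20%, the median hazard ratio is 0.56–0.57 without covariates. Adjusted for age, region and WT1 it is 0.56, 0.54, 0.51 and 0.47 (none to strong).
- The three 95% intervals disagree on excluding 1 in 7–17% of trials at 40% and 8–27% at 35%.
- With no treatment effect, at least one of the three intervals excludes 1 in 7–9% of trials.

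**The case against.** **On the test.** Protocol and SAP agree on a plain log-rank test, and the trial is sized on it. The test is valid, does not inflate type I error and delivers roughly the stated power. The gain rests on assumed prognostic strengths. The protocol's remark on age concerns AML in general, not patients aged 60 or older in first remission after consolidation, and nothing says region is prognostic. The loss with no prognostic effect (1.6–1.7 points) is close to the gain in the moderate case (1.8–2.3). The proposed strata are not the nine randomised cells; with all nine, the change is about −3, −1, +0.5 and +3 to +6 points. No calculation was made for OS. The change alters the primary test of an exploratory phase 2 protocol developed after consultation with the Japanese regulator.

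**On the estimate.** The protocol already ranks the no-covariate hazard ratio first, and SAP 4.13 describes the adjusted models as additions. The primary test is unaffected, all three models are pre-specified, and SAP 4.2 says multiplicity is not adjusted.

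**What stands.** All of this is correct as fact. It makes the first issue one of efficiency, with a conditional gain, and it means the 7–9% figure is not the error rate of the primary test. It does not remove the reason to analyse by the factors used in allocation when the downside is under 2 points. The SAP's order of models still conflicts with the protocol's ranking.

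**Conclusion.** The concern holds on both parts, and the plan should be changed. The primary DFS and OS tests name no strata despite stratified randomisation. This is neither a validity error nor a contradiction of the 53–75% power. For DFS, six strata would change power by about −2 to +7 points, depending on how prognostic age and region are, and would keep type I error near 5% where the plain test falls to 3.6%. For OS the argument carries over, but its size was not calculated. The missing main hazard ratio is a clarity gap: it leaves room for selective emphasis among three estimates whose intervals can disagree. The sizes rest on assumed prognostic effects, age split, WT1 distribution, block size and no dropout.

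**What to change.** Before unblinding:

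1. In SAP 4.7.1.1 and 4.7.2.1, make the primary DFS and OS tests log-rank tests stratified by age group (three levels) and region (Japan versus Republic of Korea + Taiwan). This pooling is already used in the SAP's Cox models and avoids very small strata.
2. Take the main hazard ratio and 95% interval from a Cox model with treatment only, stratified by the same factors.
3. Label the unstratified log-rank test and the three current Cox models as sensitivity analyses.
4. Add a row to SAP 4.13 declaring the change from Protocol 11.3.1.1 and 11.3.1.2, including the pooling of regions.

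The cost is one STRATA statement, some SAP wording and one row in 4.13, plus about 1–2 points of power if the factors turn out not to be prognostic.

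If the sponsor prefers the plain test, the minimum is to say explicitly that it is unstratified and to name the no-covariate Cox hazard ratio as the main estimate, in line with Protocol 11.3.1.1. That costs no power and adds no analysis.

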3.3.3 Exploratory

- OCV-501-specific IFN- γ production, WT1-killer peptide specific IFN- γ production, anti-OCV-501 antibody level, anti-WT1 antibody level and immunoglobulin
- WT1 mRNA level

[Rationale for endpoint selection]

[Efficacy]

Primary endpoint

This trial was planned to assess the contribution of OCV-501 to life prognosis through relapse prevention in AML patients who have completed consolidation therapy. Therefore, disease-free survival (DFS: time from randomization to AML relapse or death from any cause, whichever comes first, within the observation period) was set as the primary endpoint.

Secondary Endpoints

Overall survival (OS) was set as a general endpoint relevant to survival in anticancer drug therapy. The representative QOL and performance status surveys, EORTC QLQ-C30 and ECOG PS, were set to assess QOL and PS in subjects.

[Safety]

General tests were set out of consideration for subjects' safety and to assess the safety of OCV-501.

[Exploratory]

Measurements of OCV-501-specific IFN- γ production and WT1-killer peptide specific IFN- γ production were set to measure the helper T cell activation and WT1-killer specific T cell activation induced by OCV-501. Measurements of anti-OCV-501 antibody level and anti-WT1 antibody level were set to confirm antibody induction ability because antibody induction against the WT1 protein has been reported.³⁴ Immunoglobulin was set to monitor whole immunological changes.

Expressed level of WT1 mRNA was set because it is considered to be useful as a monitoring marker of minimal residual disease (MRD).

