4.12 Determination of Sample Size

The number of AML patients is not very high, and is estimated to be approximately 7000 in Japan⁷. From the fact that in the previous clinical trial (JALSG GML200) in elderly AML patients, it has been forecast that the possible enrollment in Japan is to be at most 70 in one year. Also, from the preliminary trial feasibility survey, it is known that around 50 subjects could be recruited in one year in the Republic of Korea and Taiwan. Through a global trial in Japan, the Republic of Korea and Taiwan, it is considered possible to enroll 120 subjects in one year to assess the efficacy of OCV-501.

Within the limitation of the past experiences with regard to IMP administration, the target sample size will be considered with reference to following publications.^{5,6,7,9} With reference to disease-free survival which has been reported from trials in AML patients 60 years or older who have received the consolidation therapy followed by maintenance therapy, the 2-year DFS rate of placebo arm has been estimated to be around 20%.^{5,6,7}

On the other hand, considering the so-called graft-versus-leukemia (GVL) effect associated with a lower relapse risk after the allogeneic hematopoietic stem cell transplantation, OCV-501 is basically expected to have the same benefits. With reference to the findings of Kurosawa et al,⁹ which have reported a 30% higher 2 or 3-year DFS in elderly AML subjects who have received the allogeneic hematopoietic stem cell transplantation compared with those without transplantation, OCV-501 is expected to have a 15% - 20% higher 2-year DFS. Under the assumption of exponential distribution of DFS time, the hazard ratio (placebo vs. OCV-501) has been set to 0.57 - 0.65, and with a two-sided log-rank test at the 5% significance level, 60 or more subjects in each treatment group can achieve a power of 53% - 75% or more to detect the difference between placebo and OCV-501 groups.

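### The primary DFS log-rank test is valid but makes no use of Day 1 WT1 mRNA; stratifying on it would be a cheap, optional gain in power if the marker is prognostic

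*SAP*

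**What the plan says.** **Primary test.** SAP 4.7.1.1: "Primary test for comparison between OCV-501 and Placebo will be conducted by Log-rank test". Protocol 11.3.1.1 also names the log-rank test as the primary method. Neither document gives it a stratum. SAP 4.7.2.1 applies the same analysis to OS.

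**The marker.** Protocol 7.1.3.1.1 has WT1 mRNA sampled on Day 1 before dosing, and Protocol 7.2.3.1 has the central laboratory measure it in all subjects. The endpoint rationale in Protocol 3.3.3 includes WT1 mRNA because "it is considered to be useful as a monitoring marker of minimal residual disease". SAP 4.13 explains why the Day 1 value replaces earlier values in the baseline table: "Day 1 data would be more influential than the data at diagnosis or at the time of induction or consolidation therapy".

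**Where the marker is used.** It enters only the Cox models in SAP 4.7.1.1, where "treatments effect will be adjusted with covariates (Age, Country/Region and WT1 mRNA level at Day 1" are the adjusters. One further model has WT1 mRNA alone and another has no covariates. The categories are fixed: <50, 50-199, 200 or more, and Unknown. SAP 4.5 also tabulates the Day 1 level by arm.

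**Randomisation.** Protocol 6.3 stratifies by country/region and age only.

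**Power.** SAP 4.12 states 53% to 75% for 60 per arm "with a two-sided log-rank test at the 5% significance level".

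**The concern.** Leaving a strong prognostic factor out of a time-to-event comparison pulls the marginal treatment effect toward the null, and the test loses sensitivity even when the arms are perfectly balanced. Nothing in the randomisation balances WT1 mRNA either. With 60 per arm, a chance difference in the share of high-marker patients passes straight into the primary p-value. Supportive Cox models can describe such an imbalance but cannot change that p-value.

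The stated power starts at 53%, so a few points matter. The variable is already collected, measured before treatment and categorised, so using it needs no extra patients or data.

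**Working it through.** **1. Reproduce the plan's power.** Inputs from SAP 4.12: "the 2-year DFS rate of placebo arm has been estimated to be around 20" per cent; "OCV-501 is expected to have a 15% - 20% higher 2-year DFS"; exponential DFS; 60 per arm. Protocol 3.2 gives two years of DFS observation. Dropout is not stated and is taken as none.

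- Hazard ratios: ln 0.35 / ln 0.20 = 0.652 and ln 0.40 / ln 0.20 = 0.569. These match the SAP: "the hazard ratio (placebo vs. OCV-501) has been set to 0.57 - 0.65".
- Events: 60 × 0.80 + 60 × 0.65 = 87, and 60 × 0.80 + 60 × 0.60 = 84.
- Schoenfeld: power = Φ(|ln HR| × √(D/4) − 1.96).
  - HR 0.652: 0.427 × 4.664 − 1.96 = 0.03, power 51.3%.
  - HR 0.569: 0.563 × 4.583 − 1.96 = 0.62, power 73.3%.

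Both are within 2 points of the stated 53% and 75%. The hazard ratios are derived from pooled arm-level DFS rates, so they are marginal effects, not effects within marker level.

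**2. Add a prognostic marker.** The marker's hazard ratio and shares are assumptions. In the simulations DFS is exponential within marker level and censored at 2 years. Baseline and treatment hazards are calibrated so that pooled 2-year DFS stays at 20% on placebo and 35% or 40% on OCV-501. Each trial is tested with the unstratified and the marker-stratified log-rank at |Z| > 1.96.

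Two-level marker, power unstratified → stratified:

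| Marker-high | Marker HR | OCV-501 DFS 35% | OCV-501 DFS 40% |
|---|---|---|---|
| 35% | 1 | 50.7% → 50.4% | 73.2% → 72.5% |
| 20% | 2 | 52.3% → 54.5% | 74.3% → 76.4% |
| 35% | 2 | 53% → 57% | 74% → 78% |
| 50% | 2 | 53% → 57% | 74% → 78% |
| 20% | 3 | 52% → 59% | 75% → 81% |
| 35% | 3 | 55% → 66% | 76% → 86% |
| 50% | 3 | 55% → 68% | 76% → 86% |

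At marker HR 1.5 the gain is about 0 to 1 point. Type I error of the stratified test stays near 5%.

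**3. Use the SAP's four categories as strata** (assumed shares 45%, 25%, 25%, and 5% Unknown):

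- Both upper categories at HR 2: 52.6% → 55.0% and 74.5% → 76.9%. At HR 3: 54.8% → 64.0% and 76.1% → 84.2%.
- Graded effect, top category at HR 2 and the middle one at √2: 52.3% → 53.4% and 74.1% → 75.3%. With the top category at HR 3: 53.4% → 59.2% and 75.0% → 80.8%.
- Uninformative marker, three equal strata: 51.5% → 50.4% and 73.2% → 71.9%, a cost of 1.1 and 1.3 points.

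**4. Chance imbalance.** With 35% marker-high, the standard deviation of the arm difference is √(2 × 0.35 × 0.65 / 60) = 0.087. A gap of 10 points or more (6 patients) arises in about 28% to 30% of trials. If 40% of OCV-501 and 30% of placebo patients are marker-high, power is as follows (OCV-501 DFS 35% / 40%):

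- Marker HR 2: unstratified 40% / 66%, stratified 56% / 79%.
- Marker HR 3: unstratified 34% / 59%, stratified 66% / 85%.

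With the same gap reversed and no drug effect, the unstratified test favours OCV-501 in 4.4% to 5.3% of trials against a nominal 2.5%; the stratified test does so in 2.4% to 3.1%. These figures are conditional on the imbalance. Averaged over randomisations, the planned test keeps its 5% level.

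**The case against.** The strongest objection is that the key input is missing. No section gives a prognostic hazard ratio for Day 1 WT1 mRNA or the share of patients in each category. This stands, so every gain above is conditional.

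A reader might infer from the SAP 4.13 wording that the sponsor regards the Day 1 value as strongly predictive of relapse. The text does not go that far. It compares Day 1 with earlier measurements, as the reason for exchanging a baseline-table variable. The protocol's description concerns monitoring, which is serial use.

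A reader might also infer that the planned test forfeits power the sponsor was counting on. At the planned pooled DFS rates it does not: the unstratified column in step 2 runs from 51% to 55% and from 73% to 76%. A shortfall appears only if 0.57 to 0.65 is read as the hazard ratio within marker level. With 50% marker-high, unstratified power is then 47% and 69% at marker HR 2, or 40% and 61.5% at HR 3. SAP 4.12 derives its hazard ratios from pooled rates, so it does not support that reading.

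Finally, WT1-adjusted Cox models are already prespecified, the unstratified log-rank is the protocol's named test and the basis of its sample size, and the synopsis labels the trial exploratory. All of this is true and lowers the priority. It leaves the primary p-value without any use of the marker.

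**Conclusion.** The plan contains no error here. The primary test is valid and delivers about its stated power. Stratifying it by Day 1 WT1 mRNA is an optional efficiency gain that also guards the primary p-value against marker imbalance.

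Its size rests on assumed marker effects with 20% to 50% of patients marker-high: about 2 to 4 points at marker HR 2 and about 6 to 13 at HR 3. It is about 0 to 2 points if the effect is weaker, or graded with only the top category reaching a doubling. The cost is about 1 to 1.5 points if the marker carries no information. The upper figure is tied to HR 3 and is not a ceiling: at HR 4, with shares of 20% to 70%, the gain is 9 to 20 points. Nothing in the documents says where in this range the trial lies.

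**What to change.** In SAP 4.7.1.1, make the primary DFS test a log-rank test stratified by Day 1 WT1 mRNA, using the four categories already defined there (<50, 50-199, 200 or more, Unknown). Do the same for OS in 4.7.2.1. Keep the unstratified log-rank as a sensitivity analysis and list the change in SAP 4.13.

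Keep the existing categories and do not merge the upper two. If the added risk sits only at 200 or more (assumed 15% of patients, HR 3, with 30% in 50-199), a cut at 50 gains nothing, whereas the SAP's categories gain about 3 points.

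Decide before unblinding and without examining DFS or OS by WT1 category, even pooled across arms. The sponsor receives WT1 results during the trial (Protocol 7.2.3.1), and SAP 4.9 plans DFS and OS curves with blinding maintained, so such a look is possible. It would make the choice of primary test depend on accrued outcomes.

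Cost: one stratification term and SAP text, about 1 to 1.5 points of power if the marker is uninformative, and a documented departure from the protocol-named primary test.
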